#### 4.3.5. Pharmacokinetic studies

Exposure-response correlation studies will be performed in a maximum of 15 participants per treatment arm (90 patients in total) (trial A: DF study). Since moxidectin is known to be better

absorbed in humans after a high-fat meal was consumed participants will receive a local high-fat breakfast prior to treatment [16]. Upon oral intake moxidectin levels in blood will be quantified with time using a micro sampling device. Therefore, capillary blood will be taken 0, 2, 4, 8, 24, and 72 hours, 7 and 28 days post-dosing (trial A). Micro sampling presents as one of the simplest, safest and least invasive study protocols. In our lab different blood micro-sampling techniques, including dried blood spots (DBS) and Mitra®, are currently under investigation to quantify moxidectin extracted in human blood samples. Following method development according to the U.S. FDA guidelines, the best protocol will be selected for the pharmacokinetic studies (i.e. DBS or Mitra®).

As yet the micro-blood sampling analysis has not been used to measure moxidectin blood levels in *S. stercoralis*, a formal validation will be performed next to the measurement of the PK values. For this purpose an additional blood sample will be taken from the venous side to demonstrate that the capillary and venous blood correlate satisfactory or to calculate the conversion coefficient. Venous blood will be withdrawn by cannulation from the same 10 adults of one treatment arm (8 mg) at identical time points post-dosing (trial A) [13, 16, 32].

In more detail, capillary blood (± 0.1 ml) will be collected by middle or ring finger tip puncture using a finger pricker (e.g. Accu-chek Softclix Pro®, Roche). Sampling will be conducted at the specified time points in doublets. A few drops of blood will be transferred at each time point on filter paper (Whatman) or on Mitra® sticks and dried for approximately 1 hour. The dried blood spot cards or Mitra® will be transported to Basel and stored properly until analysis. Moxidectin will be quantified using the validated liquid chromatography tandem mass spectrometry (LC-MS/MS) method. Drug concentrations will be calculated by interpolation from a calibration curve with a foreseen limit of quantification of approximately 1-5 ng/ml. Quality control samples will be included in the study and its measured concentrations used to determine between-run and overall precision and accuracy of the analysis.

Venous blood (± 4 mL) will be collected in EDTA covered Vacutainer® tubes through an i.v. catheter placed in an antecubital arm vein. The indwelling catheter will be inserted in the arm not earlier than 1 hour before the beginning of the blood sampling. For the purpose of keeping the catheter patent, 0.9% sodium chloride (NaCl) will be slowly infused i.v. (1 drop per 2-3 seconds). Dilution artifacts will be avoided by interrupting the i.v. 0.9% NaCl drip prior to collection of the blood sample. In addition, approximately 0.5 ml of blood will be drawn through the catheter and wasted. Directly after the collection of the required blood volume (4 ml), the Vacutainer® tubes will be slowly tilted backwards and forwards (no shaking) to solve the anti-coagulant. 1 ml of blood will be transferred in a labeled tube, within 30 minutes post sampling. The remaining blood in the Vacutainer® will be centrifuged at about 3000 rpm for 10 min and

4°C to obtain plasma, which will be pipetted in another labeled polypropylene tube. The plasma and blood tubes will be kept in an upright position at -20 °C until analysis. The concrete time points of withdrawal of each blood sample will be entered in the form.

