#### The secondary study objectives are

- 1.) To compare the efficacy based on larvae reduction rates of ascending oral moxidectin dosages in a total of 210 adults infected with *S. stercoralis*.
- 2.) To determine safety & tolerability of ascending oral moxidectin dosages in a total of 210 adults infected with *S. stercoralis*.
- 3.) To comparatively assess the efficacy based on larvae reduction rates moxidectin versus ivermectin (200 μg/kg), the current drug of choice, against *S. stercoralis* in 350 adults infected with *S. stercoralis*.
- 4.) To determine safety & tolerability of moxidectin versus ivermectin (200 μg/kg), the current drug of choice, against *S. stercoralis* in 350 adults in two countries infected with *S. stercoralis*.
- 5.) To determine pharmacokinetic parameters in 10 adults infected with *S. stercoralis*, after oral moxidectin administration of 8 mg, using venous as well as capillary blood allowing the validation of the micro sampling analysis to measure moxidectin blood levels.
- 6.) To measure moxidectin deposition and determine exposure (including Cmax, AUC and tmax)response correlation using a microsampling technology after oral moxidectin administration of 2 mg, 4 mg, 6 mg, 8 mg, 10 mg, 12 mg versus placebo in a total of 90 adults infected with *S. stercoralis*.
- 7.) To determine the population PK parameters of the optimal dose of moxidectin in the treatment of *S. stercoralis.*

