## 4.3. Trial design

Two randomized-controlled trials will be conducted; a dose-ranging study (trial A) and a parallel group study (trial B), with seven and three treatment arms, respectively to be followed-up each over a 21-28 days period. The second comparative trial will be conducted as a non-inferior study with a non-inferiority margin of 10%-points.

- (A) The DF study (Figure 1, top) is designed as a seven-armed trial including arms with ascending dose administration of moxidectin: 2 mg, 4 mg, 6 mg, 8 mg, 10 mg, 12 mg and a placebo-arm.
- (B) The parallel group study (Figure 1, bottom) is designed as a two-armed trial including one arm with a single drug administration of a standard dose of ivermectin (200  $\mu$ g/kg) and one arm with a treatment of a single best dose of moxidectin (8 mg, according to the findings in (A)). The optimal dose of findings in (A) are evaluated as the dose that is high enough to demonstrate efficacy in the target population, yet low enough to minimize safety concerns and adverse events.

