#### 6.2. Methods of recording and assessing adverse events

Patients will be kept for observation for at least 3 hours following each morning treatment for any acute AEs. During the reporting period, any unfavorable changes in the subject's condition will be recorded as adverse events, whether reported by the subject or observed by the investigator. In case of any abnormal finding, the local study physician will perform a full clinical examination and findings will be recorded. An emergency kit will be available on site to treat any medical conditions that warrant urgent medical intervention.

In addition, patients will be also interviewed by a nurse and/or a physician about the occurrence of AEs 24 hours after treatment.

Information on all AEs (onset, duration, intensity, seriousness and causality) will be immediately entered in the appropriate AE module of the CRF which is considered as a source document. For all AEs, sufficient information will be pursued and/or obtained so as to permit i) an adequate determination of the seriousness of the event (i.e. whether the event should be classified as a SAE); ii) an assessment of the casual relationship between the AE and the study treatments (i.e. whether the event should be classified as an adverse drug reaction); and iii) an assessment of intensity of AEs by the study physician.

All SAE, unexpected adverse drug reactions, or SUSARs must be reported as described in Section 6.3.

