#### 7.2. Justification of number of trial subject

(A) DF study: Since it is already known that moxidectin acts on S. stercoralis and the existence of a drug effect is known, the main aim of the study is the elucidation of the nature of the dose-response relationship. Computer simulations showed that with 30 adults enrolled in each of the 7 study arms (0, 2, 4, 6, 8, 10, 12 mg) the dose response prediction model had a median precision (one half length of the 95%-confidence intervals) of 9%-points assuming associated true cure rates of 2.5%, 30%, 55%, 75% and 85%,

90%, 95% and a loss to follow up of 10%. The sample size is also in line with the recommendations from *Klingenberg et al. 2009* [38].

*DF study - PK sampling*: The suggested sample size of 15 participants per study arm is sufficiently high to determine the key PK parameters, considering that PK variability is low. A low PK variability is a reasonable assumption when dealing with adults.

(B) Non-inferiority moxidectin versus ivermectin: The main hypothesis of this trial is that an 8 mg dose of moxidectin is non-inferior against *S. stercoralis* compared to the standard of care therapy (ivermectin). We assume a similar true CRs for moxidectin and ivermectin of 89% [15]. The sample size determination revealed, that we need 154 participants in each trial arm to demonstrate non-inferiority of moxidectin with a non-inferiority margin of 10%-points with 80 power at the 95% confidence interval (equivalent to the 97.5% lower confidence bound). To account for an expected loss to follow-up of 10%, we target to enroll 175+175 = 350 participants.

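### Trial A: PK contacts and, at 8 mg, cannulation can add recorded adverse events unevenly across arms, and section 7.3 has no summary that separates them

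*Combined protocol and SAP*

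**What the plan says.** **Who is sampled.** Section 4.3.5 states "Exposure-response correlation studies will be performed in a maximum of 15 participants per treatment arm (90 patients in total"). Section 7.2 plans trial A "with 30 adults enrolled in each of the 7 study arms (0, 2, 4, 6, 8, 10, 12 mg") and says of the PK subset that "The suggested sample size of 15 participants per study arm is sufficiently high to determine the key PK parameters". Secondary objective 6 in section 3 covers the active doses up to "12 mg versus placebo in a total of 90 adults infected with" *S. stercoralis*. No sentence excludes placebo from sampling.

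**When.** Capillary samples are taken at 0, 2, 4, 8, 24 and 72 h and on days 7 and 28. For validation, "Venous blood will be withdrawn by cannulation from the same 10 adults of one treatment arm (8 mg"), at the same times as the finger pricks. Sections 4.3.5 and 5.4 describe an indwelling catheter, a saline drip and 4 mL draws, four on day 1 and four over the following 28 days.

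**How adverse events are collected.** Sections 4.3.3, 6.1 and 10.1 and Table 1 give every participant interviews at 3 h, 24 h and day 28, after at least 3 h of observation. Section 6.2 adds that unfavourable changes during the reporting period "will be recorded as adverse events, whether reported by the subject or observed by the investigator".

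**How they are used.** Section 7.3 summarises, descriptively, the difference between the proportions reporting events before and after treatment. It does not limit the count by time point or by cause. Section 4.3 defines the optimal dose as one high enough to be effective, "yet low enough to minimize safety concerns and adverse events".

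**The concern.** A proportion with any adverse event depends on how often participants are seen as well as on the drug. Two features of the PK sub-study can differ by arm.

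- **Contacts.** Sampled participants meet staff at times when other participants do not. If placebo participants are not sampled, that additional opportunity to have an event noted exists only on active drug.
- **Procedure.** A catheter, a drip and eight 4 mL draws fall on 10 adults in one arm. Section 5.4 itself provides daybeds in case someone feels unwell, and section 2 lists hypotension and dizziness among moxidectin's side effects. A reaction to the procedure could therefore look like a drug effect at 8 mg.

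At stake is the reading of secondary objective 2 (safety and tolerability of the ascending doses) and the adverse-event half of the optimal-dose definition. The baseline interview precedes all of this, so any excess passes unchanged into the before-after difference of section 7.3.

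**Working it through.** **1. The plan's own total.** Inputs: at most 15 per arm (4.3.5) and 7 arms of 30 (7.2).
- Six active arms: 6 × 15 = 90, which matches.
- All seven arms: 7 × 15 = 105, which does not.
- 90 spread over seven arms: 90 / 7 = 12.9 per arm. This respects the maximum of 15 in 4.3.5 but not the 15 per study arm in 7.2.

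Six arms is the likelier reading. It is an inference, and objective 6 contradicts it.

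**2. Contacts after dosing.**
- Common interviews: 3 h, 24 h, day 28, so 3 in every arm.
- PK times after dosing: 2, 4, 8, 24 and 72 h, days 7 and 28.
- PK times that are not interview times: 2, 4, 8 and 72 h and day 7. The 2 h sample lies within the 3 h observation of all participants, which leaves up to four new contacts: 4 h, 8 h, 72 h and day 7.
- Section 5.4 mentions lunch and going home at the end of the treatment day, so the 4 h contact, and perhaps the 8 h one, may not be special to PK participants. The clear additions are 72 h and day 7.

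Mean contacts per participant:
- Six-arm reading, four new contacts: 3 + 4 × 15/30 = 5.0 on active drug, 3.0 on placebo.
- Six-arm reading, two new contacts: 3 + 2 × 15/30 = 4.0 against 3.0.
- 90 spread evenly over seven arms, four new contacts: 3 + 4 × 12.9/30 = 4.7 in every arm, with no imbalance.
- 8 mg against the other active arms: no difference, because cannulation uses the same time points.

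**3. Possible effect of contacts (illustration).** The documents give no detection rates. Assume a proportion b reports an event at the common interviews, and each of k extra contacts turns a participant without an event into one with an event with probability q. On the six-arm reading the active-minus-placebo difference rises by

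(15/30) × (1 − b) × [1 − (1 − q)^k].

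- k = 4, b = 0.20, q = 0.03: 0.5 × 0.80 × (1 − 0.885) = 0.046, or 4.6 points.
- k = 4, smallest case (b = 0.30, q = 0.01): 0.5 × 0.70 × 0.0394 = 1.4 points.
- k = 4, largest case (b = 0.10, q = 0.10): 0.5 × 0.90 × 0.344 = 15.5 points.
- k = 2, b = 0.20, q = 0.03: 0.5 × 0.80 × (1 − 0.941) = 2.4 points.

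**4. Possible effect of cannulation (illustration).** If a proportion r of the 10 cannulated adults has a reaction, the 8 mg proportion rises by at most (10/30) × r. For r = 0.10 to 0.30 this is 3.3 to 10 points. The upper value needs every reaction to occur in someone who would otherwise report nothing.

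**5. Scale.** For two arms of 30 at a 20% rate, the 95% half-width of a difference is 1.96 × √(2 × 0.2 × 0.8 / 30) = 0.20, or 20 points.

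**The case against.** The strongest reply is that active ascertainment is already equal: every arm is questioned at 3 h, 24 h and day 28, and no section schedules adverse-event questions at a PK-only time. Section 6.2 concerns unsolicited events, and that route is open to everyone, since all participants receive a card with investigators' telephone numbers (5.4). Much of what is noted at a PK visit would be recalled at the next common interview. This stands. A reader might infer that events are looked for more often on drug, but the documents support only unequal opportunity for incidental recording, and only if placebo is not sampled.

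A reader might also infer that observation is most frequent at 8 mg. It is not. What is particular to 8 mg is the procedure.

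A third inference is that being sampled tells participants they are on active drug. The documents do not say what participants are told about which arms are sampled, and section 4.2 calls the PK sub-studies single blinded, so this cannot be asserted.

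Section 6.1.3 already weighs trial procedures when judging relatedness. That helps at case level, but relatedness does not enter the count in 7.3.

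Finally, the analysis is descriptive with no between-arm test, the illustrative middle case of 4.6 points is small beside a half-width of 20, and the protocol already names 8 mg for trial B although a cannulation artefact would count against it. This limits the consequence. It does not remove it: such a bias has a known direction, whereas sampling error does not.

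**Conclusion.** The point holds in a limited form. Two things follow from the text alone: the number of sampled arms is stated inconsistently, and cannulation is confined to 10 of about 30 adults at 8 mg while 7.3 counts events whatever their cause. A third is conditional: if placebo is not sampled, up to 15 of 30 participants in each active arm have between two and four extra contacts at which events can be recorded, and placebo participants have none.

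The size is unknown. Under the assumed rates above, contacts add roughly 1 to 16 points to the active-placebo difference with four extra contacts, and less with two. Cannulation adds at most 3 to 10 points at 8 mg. Both ranges rest on assumed rates, and the documents do not show that dose selection was distorted. The practical gain is a cleaner safety report, at very little cost.

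**What to change.** 1. In section 4.3.5 and secondary objective 6, state whether placebo participants are PK-sampled, and make the total of 90 agree with the answer.
2. In section 7.3, keep the summary of all adverse events for each arm. Beside it, add a between-arm summary based on the interviews common to all 210 participants (3 h, 24 h, day 28). Say that an event already noted at a PK contact still counts there if it is also reported at a common interview, so that the restriction does not bias the comparison the other way.
3. Tabulate separately the events first noted at PK-only contacts and those attributed to finger prick or cannulation.
4. Show the 8 mg arm with and without procedure-attributed events.
5. Add a field to the adverse-event form for sampling procedure as a cause, and one for the contact at which the event was first noted if the form's dates do not already give it.

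The cost is one extra table and a small change to the form. No visits are added. No safety data are dropped, because the all-event summary stays. That matters, since a restricted summary used alone would discard spontaneous reports and real events seen at PK contacts.

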Second, to date pharmacokinetic studies of moxidectin have been conducted exclusively in a low number of healthy adults and consequently the pharmacodynamic behavior of moxidectin is completely unknown. [13, 16]. Yet, a PK characterization is central to understand the human body's response to a drug, especially in populations that physiologically differ from healthy adults. Physiological abnormalities like mal- or undernutrition and intestinal worms, such as *S. stercoralis*, can potentially affect the PK of a drug [17, 18]. Being minimal invasive, minimal painful, simple and rapidly performed, micro-blood sampling (e.g. the dried blood spot (DBS)) has developed into the method of choice for PK studies and will be also used in this study. Micro-blood sampling has been repeatedly proven to correlate well with the standard method that uses venous blood [19-22]. Micro blood sampling analysis has not been used to measure moxidectin blood levels and, therefore, requires a validation. For this purpose, a formal validation, using blood samples from two vascular sides, will be performed in parallel; supporting and confirming the linearity between venous and capillary blood also for moxidectin.

Last, it would be crucial to elucidate if moxidectin at an appropriate dose could serve as an alternative to ivermectin, which is to date one of the very few but the drug of choice against *S. stercoralis.* 

In view of remaining knowledge gaps of the optimal doses of moxidectin against *S. stercoralis* as well as insufficient evidence on safety and efficacy parameters our study aims in a first step to thoroughly investigate the efficacy and safety of ascending doses of moxidectin (2 mg, 4 mg, 6 mg, 8 mg, 10 mg, 12 mg versus placebo) against *S. stercoralis* infection, complemented by PK studies. Once the optimal dose of moxidectin has been identified in this phase 2a trial (trial A: DF study), we aim in a second study to compare the safety and efficacy of the single best dose of moxidectin to the standard dose of ivermectin in two phase 2b trial settings (trial B: parallel group study). This study will be complemented by assessing socioeconomic factors, household characteristics and behaviors, using a household questionnaire. Moreover, we will inform about potential environmental risk factors.

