#### 5.4. Treatment of subjects

2 mg tablets of moxidectin will be obtained from Medicines Development for Global Health (MDGH), Australia. Ivermectin (3 mg) will be purchased from Merck, Switzerland. Matching placebo tablets (moxidectin and ivermectin) will be obtained from the Medicines Development for Global Health (moxidectin) and produced and a certificate of manufacture and analysis provided by the University of Basel (ivermectin). The appropriate doses will be calculated and the correct amount of moxidectin and placebo (trial A) and moxidectin, moxidecin placebo or ivermectin or ivermectin placebo tablets (trial B) will be administered to all participants. Due to blinding the tablets will be repacked into neutral separate opaque plastic bags each containing the adequate dose of moxidectin tablets and/or placebo tablets (trial A). In trial B, the tablets will be handed out from the drug container according to the randomization list. Each person will receive (i) either 4 moxidectin or 4 moxidecin placebo tablets and (ii) the number of ivermectin tablets with regard to their weight category or the corresponding number of ivermectin placebo tablets. The tablets will as long as applicable be stored in the original package and at any time (except treatment day) be stored according to manufacture prescription, sealed and away from light.

The principal investigator(s) or co-investigator(s) is responsible for drug accountability at the study site. Maintaining drug accountability includes careful and systematic study drug storage, handling, dispensing and documentation of administration.

Treatment and blood sampling (capillary blood sampling for a total of 90 participants, in trial A and venous blood sampling for 10 patients (trial A)) will be done community-based in local temples, that are quiet and spacious locations, where people like to gather and organize meetings. Infrastructure as required for the study needs (i.e tables, chairs, a fridge, a cover from rain and sun) will be installed as necessary at the specific study days. Opportunities

(approximately three daybeds) will be provided to comfortably withdraw the venous blood (4 samples on day 1 and 4 samples within the next 28 days) and to provide a possibility to lie down in case of an arising unwell feeling. Participants will receive a breakfast two hours prior to treatment as well as lunch during the day once absorption of the drug is complete.

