#### 7.3. Description of statistical methods

An available case analysis (full analysis set according to the intention to treat principle) will be performed, including all subjects with primary end point data. Supplementary, a per-protocol analysis will be conducted. CRs will be calculated as the percentage of worm-positive adults at baseline who become worm-negative after treatment. LPG will be assessed by calculating the mean of the larvae counts from the three duplicate Baermann assays and relate this value to the mean weighted amount of stool sample. The LRR will be calculated (LRR = (1-(mean at follow-up/mean at baseline))\*100).

AEs will be evaluated descriptively as the difference of proportion reporting adverse events before and after treatment.

Trial A:  $E_{max}$  models using the Dose Finding package of the statistical software environment R will be implemented to predict the dose-response curves in terms of CRs and LRRs. Noncompartmental and nonlinear mixed-effects (NLME) modeling will be used to determine pharmacokinetic parameters.

On the basis of the LC-MS/MS measurements, the following PK parameters for plasma, whole blood and capillary blood will be calculated:

• Cmax maximal plasma concentration

- tmax time to reach Cmax
- AUC area under the curve, from 0 to 24h and 0 to inf.
- t1/2 elimination half-life

 $C_{max}$  and  $t_{max}$  will be observed values derived from the plasma concentration time profile. AUC and  $t_{1/2}$  will calculated with the software WinNonlin (Version 5.2, Pharsight Corporation, USA) using compartmental analysis. The elimination half-life will be estimated by the equation:  $t_{1/2} = ln2/\lambda$ , where  $\lambda$  will be determined by performing a regression of the natural logarithm of the concentration values during the elimination period.

Trial B: The non-inferiority margin is set to 10%-points, i.e. if the lower bound of the 95% CI of the differences in cure rates is greater than -0.1 we conclude that moxidectin is non-inferior to ivermectin. The 95% confidence interval of the differences in CRs will be estimated using the standard formula:

 $CI = (CR_{mox} - CR_{iver}) + - Z_{a/2} * \sqrt{(SE_{mox}^2 + SE_{iver}^2)}.$ 

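### Capillary sampling may be accepted on correlation, which a constant capillary/venous ratio does not affect, and no rule says when the conversion coefficient is applied

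*Combined protocol and SAP*

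**What the plan says.** Section 4.3.5 plans capillary sampling in a "maximum of 15 participants per treatment arm (90 patients in total"). The schedule is fixed: "capillary blood will be taken 0, 2, 4, 8, 24, and 72 hours, 7 and 28 days post-dosing". For validation, "Venous blood will be withdrawn by cannulation from the same 10 adults of one treatment arm (8 mg) at identical time points post-dosing". Section 5.4 gives the same number of venous samples, "4 samples on day 1 and 4 samples within the next 28 days".

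The purpose of the venous samples is to "demonstrate that the capillary and venous blood correlate satisfactory or to calculate the conversion coefficient". Section 2 describes the same exercise as "supporting and confirming the linearity between venous and capillary blood also for moxidectin", and supports microsampling in general as "proven to correlate well with the standard method that uses venous blood".

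In section 7.3, "the following PK parameters for plasma, whole blood and capillary blood will be calculated". That section defines Cmax as a plasma concentration and takes Cmax and tmax from the plasma profile. Neither section names a statistic for comparing the sites, an acceptance limit, or a rule for applying a conversion to the capillary data. The quality control samples in section 4.3.5 address the precision and accuracy of the LC-MS/MS assay, which is a different question from agreement between sampling sites.

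**The concern.** Correlation and linearity show whether two measurements move together, not whether they give the same value. Over a full concentration-time profile, both sites rise and fall with the drug, so the correlation will be high even if one site reads consistently above the other. If satisfactory correlation is enough to accept capillary values as they stand, the conversion coefficient need never be applied.

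Most of the PK data depend on this step. Only 10 adults in one arm have venous blood, and the others have no plasma, although Cmax and tmax are defined on plasma. Section 2 justifies the PK work by the possibility that infected adults differ from the healthy adults studied so far, and says microsampling has not been used for moxidectin before. An uncorrected ratio between matrices could therefore be mistaken for a difference between populations. In addition, the synopsis lists a comparison of exposure-response in venous and capillary blood as a secondary objective, and section 7.3 gives no method for it.

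**Working it through.** **1. Counts (sections 4.3.5 and 5.4)**

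- PK participants: 15 × 6 active arms = 90, which reproduces the plan's figure. With the placebo arm it would be 15 × 7 = 105. Secondary objective 6 in section 3 names placebo alongside the 90, but this does not change the point.
- Capillary samples only: 90 − 10 = 80.
- Venous times per adult: 4 + 4 = 8. Pairs: 10 × 8 = 80, of which 10 × 7 = 70 are post-dose.

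The plan gives no correlation threshold, bias limit or precision target for the validation, so there is no such figure to reproduce.

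**2. Correlation under a constant bias**

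Let V be the venous and C = a + bV the capillary concentration, with b > 0. Then corr(V, C) = b·Var(V) / [SD(V) · b·SD(V)] = 1 for every a and every b > 0. Linearity is also perfect. Neither property can reveal b ≠ 1 or a ≠ 0.

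**3. The same with measurement noise**

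The simulation used 10 adults × 7 post-dose times and 1,000 data sets per setting. All of the following inputs are assumptions:

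- a bi-exponential profile of 45.0, 51.9, 49.1, 34.1, 15.0, 8.6 and 4.6 ng/ml at the seven times;
- a between-subject SD of log exposure of 0.2 or 0.4;
- noise of 10% or 15% in each matrix.

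Each range covers the medians of the four combinations.

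| Capillary relative to venous | Pearson r | Lin's concordance | Geometric mean ratio | AUC ratio |
|---|---|---|---|---|
| equal | 0.935–0.975 | 0.932–0.974 | 1.00 | 1.00 |
| × 0.7 | 0.934–0.975 | 0.777–0.832 | 0.70 | 0.70 |
| × 1.3 | 0.935–0.975 | 0.843–0.891 | 1.30 | 1.30 |
| × 1.5 | 0.935–0.976 | 0.740–0.796 | 1.50 | 1.50 |
| + 5 ng/ml | 0.927–0.973 | 0.898–0.951 | 1.32–1.33 | 1.47–1.50 |

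Pearson r is essentially the same in the first four rows. The geometric mean ratio recovers each proportional bias from the same samples.

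**4. What a proportional bias b changes**

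- Cmax and AUC are multiplied by b.
- Apparent clearance (dose/AUC) and apparent volume are divided by b. With b = 1.3, clearance is 1/1.3 = 0.77 of its true value.
- ln(bC) = ln b + ln C, so the terminal slope λ and t½ = ln 2/λ are unchanged. tmax is also unchanged.
- Every capillary exposure is multiplied by the same b, so ranking and within-trial correlation with response are unchanged. Only the scale of the exposure axis moves.

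An additive bias is different. ln(C + a) is not a shifted ln C, so half-life and AUC to infinity are distorted too.

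**5. Can 10 adults estimate the ratio?**

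The 95% CI factor is exp(± t(0.975; 9) × SD/√10), with t = 2.262 and SD the between-subject SD of the log ratio (assumed).

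- SD 0.10: half-width 2.262 × 0.10/3.162 = 0.072, factor 0.93 to 1.07.
- SD 0.30: half-width 0.215, factor 0.81 to 1.24.

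The planned pairs can therefore estimate a bias, well or only roughly depending on that SD.

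**The case against.** **The sentence also names a conversion coefficient.** This is the strongest counter-argument. A reader might infer that conversion is reserved for poor correlation. The text does not say so: the two aims are joined by a bare or. A single coefficient is in fact most useful when the sites track each other but differ by a ratio, so the authors evidently had a systematic difference in mind. This part of the objection stands, and it limits the point to a missing trigger and a possible, not certain, lack of correction.

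**No statistic is named.** The plan specifies neither Pearson r nor a threshold. The simulation illustrates what a correlation rule would do and is not evidence about real moxidectin data. That is fair, but step 2 of the working is algebra and does not depend on the assumed profile or noise.

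**A bias might be noticed anyway.** A reader might infer that the plan is blind to a large difference. That goes too far. Parameters are calculated separately for plasma, whole blood and capillary blood, so the 10 paired adults would have comparable Cmax and AUC values. However, nothing tells the analyst what to do on seeing a difference.

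**Exposure-response.** A reader might infer that the exposure-response findings would be wrong. If the analysis uses capillary values throughout, a constant ratio leaves the association intact. Only an additive or concentration-dependent bias could distort it further.

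**Conclusion.** The point holds in a limited form. The acceptance criterion in section 4.3.5 and the linearity aim in section 2 cannot detect a constant capillary/venous ratio, and no other section adds an agreement analysis or a rule for applying the conversion. On one natural reading, uncorrected capillary values could be reported for 80 of the 90 PK participants. Their Cmax and AUC would be off by the full ratio, and apparent clearance and volume by its inverse.

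The ratios of 0.7 to 1.5 are illustrations. The documents give no value for moxidectin and do not support a claim that a bias of that size exists. PK parameters are secondary endpoints under section 4.1, so the cure-rate analyses of both trials are untouched. This is a worthwhile improvement in method, not a threat to the main conclusions.

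**What to change.** In sections 4.3.5 and 7.3, make agreement the criterion and keep correlation as a descriptive figure.

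- **Model.** From the paired post-dose samples of the 10 adults, model the log capillary/venous ratio with a participant random effect and time. Do this separately against venous whole blood and against plasma, because the conversion factor depends on the reference and section 7.3 takes Cmax and tmax from plasma.
- **Report.** Give the geometric mean ratio with 95% CI and the 95% limits of agreement, and check for a trend across concentration.
- **Decide.** Use capillary values unconverted only if the whole 95% CI lies inside an acceptance range stated in advance. A CI that crosses a limit does not count as agreement. Otherwise apply the estimated conversion to all capillary data and also report the unconverted values.
- **Timing.** Fix the rule before the paired concentrations are examined. The synopsis already names the dose carried forward from trial A, so those data may exist. If they have been examined, report the rule as post hoc.

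The cost is analysis wording and a little more analysis, with no new participants, samples or visits. The drawback is that a conversion factor from 10 adults in one dose arm may be imprecise, as the range of 0.81 to 1.24 at an assumed SD of 0.30 shows. The CI should therefore be reported alongside any converted exposures.
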